## **Adverse Events and Data Monitoring Committee(DMC)**

- Patients will be instructed to call immediately with any adverse events. All adverse events will be recorded during the administration of H.P. Acthar. Any serious adverse events will be reported immediately to the appropriate contact person at Questcor, as well as to the IRB in accordance with their policy.
- A DMC will not be used because H.P. Acthar is an approved drug for treatment of dermatomyositis.

- A DRC is not planned given that Acthar is currently used in clinical medicine to treat multiple sclerosis and has a well-known adverse effect profile with low risk of significant adverse events.
- An interim analysis is not planned.

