## **Background and Significance**

H.P. Acthar gel (adrenocorticotropic hormone gel) received FDA approval for treatment of a variety of diseases, including dermatomyositis, in 1952. Despite this there is a paucity of clinical data concerning the efficacy of H.P. Acthar gel for treating dermatomyositis. Recently a small, retrospective case series describing significant improvement in both cutaneous and musculoskeletal symptoms in 5 patients with refractory dermatomyositis treated with H.P. Acthar gel was reported and has resulted in renewed interest in use of this medication in dermatomyositis patients (3). The proposed efficacy of H.P. Acthar gel has been attributed to its unique ability to induce production of endogenous cortisol, corticosterone, aldosterone, and to bind melanocortin receptors on lymphocytes and other cells to modulate immunologic responses. Our hypothesis is that H.P. Acthar gel will be safe and effective for treating the cutaneous manifestations of dermatomyositis in patients with refractory classic dermatomyositis, juvenile dermatomyositis, and amyopathic dermatomyositis.

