## **Research Procedures**

- 1) Upon enrollment patients will undergo a thorough history (including assessing time of diagnosis), review of systems, and a complete physical examination.
- 2) A detailed examination of the skin and mucous membranes will be performed, noting for presence/absence of the following: scalp erythema and atrophy, heliotrope rash, typical erythema and atrophy of sun-exposed areas on the neck, upper chest and upper back (shawl sign), erythema +/- scaling of the elbows and/or knees (Gottron's sign), gottron's papules, periungual erythema, ragged cuticles, proximal nailfold capillary loops, palmar scaling and hyperkeratosis (mechanic's hands), a rash involving the hips (holster sign), oral ulcerations, cutaneous ulcerations, purpura.
- 3) Objective cutaneous dermatomyositis scoring by the primary investigator using the **modified Cutaneous Dermatomyositis Disease Area and Severity Index** (CDASI) score and **Abbreviated Cutaneous Assessment Tool** (aCAT) will be performed at each visit ([8-13](#)).
- 4) Objective general cutaneous disease scoring by the primary investigator using the **Physician Global Activity** for (a) **overall skin** (b) **skin activity** (c) **skin damage** will be performed at each visit (each assessed using both VAS-0-10 visual analog scale and Likert scale- 0-4 for each) ([9](#)).
- 5) Objective scoring tools to be completed by the patient at each visit will include: **Patient Global Assessment (Skin) Score** (0-10 visual analog scale), **Patient Global (Itch) Score** (0-10 visual analog scale), and the **Dermatology Life Quality Index** (validated quality of life assessment) ([8-12](#)).
- 6) Photographs of all cutaneous lesions will be performed at baseline and at each follow-up visit.
- 7) Evaluation for current presence of myositis will be performed using the **Manual Muscle Testing 8 (MMT-8)** scoring tool by the primary investigator, as well as with serologic studies below ([11, 12](#)).
- 8) Completion of the **Myositis Disease Activity Assessment Tool** (MDAAT) by the primary investigator to assess disease activity of extramuscular organ systems ([12](#)).
- 9) Serologic studies at baseline will include an AM cortisol level, CBC w/ diff, CMP, CK, aldolase, LDH, comprehensive myositis panel (ARUP labs), C3, C4, and HbA1c. The above serologic studies (except for the comprehensive myositis panel) will be repeated at the final visit.

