10) Patients may continue their current immunosuppressive treatment regimens at the time of starting H.P. Acthar. If it is felt that patients should taper off of medications they will require a washout period:

- corticosteroids- 2 weeks
- methotrexate/azathioprine/mycophenolate/cyclosporine/sirolimus- 4 weeks
- adalimumab/infliximab/IVIG/chlorambucil/cyclophosphamide- 8 weeks
- rituximab- 6 months.

They will be instructed to continue topical medications, moisturizers, and sunscreen based on their current practice, which will be recorded at baseline and during subsequent visits.

11) All patients will receive 80 U (1 mL) of H.P. Acthar gel via subcutaneous injection twice weekly for 24 weeks (approximately 6 months).

12) Patients will require **follow-up visits in person at 1mo (+/- 5 days), 3mo (+/- 5 days), and 6mo (+/- 5 days)** after initiation of the H.P. Acthar, at which time examinations and clinical scoring tool assessments will be repeated.

13) If corticosteroids are continued in patients receiving H.P. Acthar gel they will be tapered at the primary investigator's discretion based on clinical evaluation at follow-up appointments.

14) H.P. Acthar will be discontinued in any given patient at the primary investigator's discretion if deemed necessary for the patient's overall health and well-being at any point during the study.

Serologic Studies	Baseline	6mo
CBC w/ diff	X	X
CMP	X	X
AM cortisol level	X	X
Creatine Kinase	X	X
Aldolase	X	X
LDH	X	X
C3	X	X
C4	X	X
HbA1c	X	X
Comprehensive myositis panel (ARUP labs)	X	

Length of above tests is that of a typical phlebotomy blood draw.

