#### **2. Secondary end-points:**

a) Statistically significant change in **MDAAT** Score and **MMT-8** score

---

Protocol Version Date 7/30/14

- b) Statistically significant change in **Global Patient Score**, **Global Itch Score**, and/or the **Dermatology Life Quality Index scores** between baseline and 6 months.
- c) Safety and tolerability of H.P. Acthar gel based on frequency and types of adverse effects.
- d) median/mean change in glucocorticoid dose from initiation to completion of study.
- e) median/mean change in dose of systemic steroid-sparing immunosuppressive agents from initiation to completion of study.
- f) median/mean change in HbA1c

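### Adverse events are found only through the patient's own call: no enquiry is listed at the 1-, 3- and 6-month visits, so safety end-point c) may under-count gradual, non-serious events

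*Combined protocol and SAP*

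**What the plan says.** Safety is part of the study hypothesis in Background and Significance: "Our hypothesis is that H.P. Acthar gel will be safe and effective". It becomes secondary end-point c): "Safety and tolerability of H.P. Acthar gel based on frequency and types of adverse effects".

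The section Adverse Events and Data Monitoring Committee (DMC) describes collection in three steps. First: "Patients will be instructed to call immediately with any adverse events". Then: "All adverse events will be recorded during the administration of H.P. Acthar". Serious events have their own route: "Any serious adverse events will be reported immediately to the appropriate contact person at Questcor", and also to the IRB. The same section plans no DMC, no DRC and no interim analysis.

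Research Procedures item 1 ties history and review of systems to the start: "Upon enrollment patients will undergo a thorough history (including assessing time of diagnosis), review of systems, and a complete physical examination". Item 12 sets in-person visits at 1, 3 and 6 months, "at which time examinations and clinical scoring tool assessments will be repeated". The clinical-assessments table lists nine instruments at baseline and each visit, the MDAAT among them. It has no row for adverse events, blood pressure or weight. Laboratory tests are done at baseline and 6 months, and change in HbA1c is secondary end-point f). Statistical Methods names no analysis specific to adverse events.

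**The concern.** A commitment to record all events is not a method of finding them. The one method stated is passive: the patient must notice an effect, judge it worth a call, and call. Serious or abrupt events will usually pass that filter. Slow or mild ones may not, and patients see the team in person only three times after starting treatment.

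The protocol itself gives a reason to look for slow effects. Background and Significance says the drug stimulates the body's own production of cortisol and aldosterone, and the exclusion criteria name uncontrolled hypertension. Yet neither blood pressure nor weight is listed as a recorded variable.

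With 10 to 15 patients, one or two missed reports can decide whether an effect appears in the results at all. What is at stake is how complete the frequencies in end-point c) are, and so how they can be read against the hypothesis. Events that nobody asked about during the study cannot be reliably recovered afterwards.

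**Working it through.** **Step 1. Where could an event enter the record?**

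| Possible source | What the protocol states |
|---|---|
| Patient call | Stated, for any adverse event |
| History and review of systems | Stated for enrollment only (item 1) |
| Question at 1, 3 or 6 months | Not stated in item 12 or in the assessments table |
| Examination at visits | Repeated (item 12); no blood pressure or weight listed as data |
| MDAAT at visits | Repeated; scores disease activity outside the muscles, not adverse events |
| Laboratory tests, HbA1c | Once after baseline, at 6 months |

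The call is the only stated route for symptomatic, non-serious events. The last three rows can reveal some problems without a call, but none is an adverse-event enquiry.

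**Step 2. The plan's own figure.** No figure is given for safety; the sample size comes from the CDASI. Its lower end reproduces. With CV 0.6 and r = 0.25, the log-scale variance is ln(1 + 0.6²) = 0.3075, the SD of the difference is √(2 × 0.3075 × 0.75) = 0.679, and a 50% decrease is ln 2 = 0.693. A two-sided paired t-test at 0.05 then needs 10 patients (power 81.9%). So 10 and 15 are taken below as the planned size.

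**Step 3. Effect of incomplete capture.** Let p be the true proportion of patients with a given event and c the chance that an affected patient's event is recorded. Neither is in the documents; both are assumed. With independent patients, the chance of recording no event is (1 − pc)ⁿ.

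For p = 0.20:
- full capture: 0.8¹⁰ = 10.7%; 0.8¹⁵ = 3.5%
- half capture: 0.9¹⁰ = 34.9%; 0.9¹⁵ = 20.6%

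Range over other assumed values (chance of recording none, n = 10 / n = 15):

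| True rate p | c = 1 | c = 0.75 | c = 0.5 | c = 0.25 |
|---|---|---|---|---|
| 10% | 34.9% / 20.6% | 45.9% / 31.1% | 59.9% / 46.3% | 77.6% / 68.4% |
| 20% | 10.7% / 3.5% | 19.7% / 8.7% | 34.9% / 20.6% | 59.9% / 46.3% |
| 30% | 2.8% / 0.5% | 7.8% / 2.2% | 19.7% / 8.7% | 45.9% / 31.1% |

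**Step 4. What zero events would show with full capture.** The exact two-sided 95% upper limit for 0 of n is 1 − 0.025^(1/n): 30.8% for n = 10 and 21.8% for n = 15. This limit comes from the number of patients, not from how events are collected.

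**The case against.** The strongest reply is that the protocol promises to record every adverse event during administration, without limiting this to events that are phoned in. The call instruction can be read as prompt notice between visits. The visits are also more than skin, muscle and quality-of-life scoring: examinations are repeated, the MDAAT is a multi-system assessment by the investigator, and item 13 refers to clinical evaluation at follow-up. The 6-month laboratory tests do not depend on calls.

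Most of this stands, and it rules out several stronger readings that a reader might infer:

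- *Only phoned-in events count.* Not supported. The call is the only stated way of finding events, not a stated limit on what is recorded.
- *No one asks about adverse events at visits.* Not supported. The protocol is silent, which is not exclusion, and blood pressure may be taken as part of an examination.
- *Events are under-counted.* Not supported as fact, because no capture rate is given.
- *The words adverse effects in end-point c) bring in an attribution step by an unblinded investigator.* Not supported. There is no causality rule, and the adverse-event section itself uses both terms loosely.

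What the reply does not remove is that nothing requires the question to be asked. Where the authors want an item recorded at each visit they say so, as item 10 does for topical treatments. Good site practice may fill the gap, but perhaps unevenly across patients and visits. One laboratory set at 6 months would not detect most symptomatic events.

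**Conclusion.** The point holds as a gap in ascertainment. Followed as written, the plan collects non-serious events passively, and end-point c) may under-count the gradual ones. Under the assumed 20% rate, moving from full to half capture raises the chance of recording none from 10.7% to 34.9% with 10 patients, and from 3.5% to 20.6% with 15. These figures assume independent patients and one common capture rate. They illustrate sensitivity and do not estimate what will happen.

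A reader might also infer that passive collection is the reason a clean result could not establish safety. The documents do not support that link. With 10 to 15 patients and no control arm described, zero events leaves up to 30.8% or 21.8% unexcluded even with perfect capture, so better collection would not by itself establish safety. Nor is there a safety test or threshold to overturn: end-point c) is a description of frequency and type.

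This is a cheap improvement to a descriptive secondary end-point and does not invalidate the design.

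**What to change.** 1. At the existing 1-, 3- and 6-month visits, add a non-leading adverse-event question followed by a short checklist, and give it a row in the assessments table.
2. Record blood pressure and weight as data at baseline and each visit. This concerns data collection only and sets no clinical threshold.
3. Use one term, adverse events, in end-point c) and in the adverse-event section, and count events regardless of attribution.
4. In Statistical Methods, state that per-patient frequencies will be reported with exact 95% confidence intervals.
5. Separately, state that zero events would leave an exact two-sided upper limit of 30.8% (10 patients) or 21.8% (15 patients) even with full capture, so end-point c) is descriptive.

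The cost is a few minutes per existing visit, one form and a few sentences. The downside is more minor events on record.

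### Adverse-event recording is stated only for the time on drug, so non-serious events after an early stop can be left out of the safety endpoint

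*Combined protocol and SAP*

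**What the plan says.** The section Adverse Events and Data Monitoring Committee makes three statements on collection and reporting:

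- "Patients will be instructed to call immediately with any adverse events". No start or end date is attached.
- "All adverse events will be recorded during the administration of H.P. Acthar". This is the only recording period in the document.
- "Any serious adverse events will be reported immediately", to the company and the IRB. No time limit is attached.

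Research Procedures supplies the timetable. Item 11 gives the drug "via subcutaneous injection twice weekly for 24 weeks (approximately 6 months"). Item 12 requires "follow-up visits in person at 1mo (+/- 5 days), 3mo (+/- 5 days), and 6mo (+/- 5 days"), counted from initiation of the drug and not from the last dose. Item 14 lets the investigator discontinue the drug if this is needed for the patient's health and "well-being at any point during the study". Item 12 does not exempt a patient who has stopped, and item 14 describes no follow-up after a stop.

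Secondary end-point c) is "Safety and tolerability of H.P. Acthar gel based on frequency and types of adverse effects". The clinical assessment table has no adverse-event row, and Statistical Methods gives no rule for counting events or for time at risk.

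**The concern.** Safety is half of what the study sets out to show: "Our hypothesis is that H.P. Acthar gel will be safe and effective". A frequency of adverse effects needs a defined observation period. The only one stated ends with the drug, while the visits run on to 6 months. A patient can therefore be off the drug, still attending visits, and outside the stated recording period.

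End-point c) does not say that it is limited to time on drug. A reader of the results would not know whether a non-serious event that appeared after a stop had been looked for, recorded and counted. Patients stopped on health grounds have the longest time outside the period, and they matter most for tolerability. In a study of about 10 to 15 patients, a single event can change the reported frequency or the list of event types.

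**Working it through.** The plan gives no figure for this point, so there is nothing to reproduce. The check has two parts.

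**1. Does any text extend recording past the last dose?**

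| Text | Time limit | Says that non-serious events after the last dose are recorded? |
|---|---|---|
| Recording sentence | Time on drug | No |
| Call-in instruction | None stated | No; it covers the patient's call, not what is recorded |
| Serious-event sentence | None stated | No; serious events only |
| Item 12, visit content | Visits to 6 months | No; examinations and scoring tools |
| Clinical assessment table | Visits to 6 months | No adverse-event row |

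None does. The gap concerns non-serious events only.

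**2. How much time is involved?**

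Inputs: the course is 24 × 7 = 168 days (item 11), and each visit has a window of 5 days either side (item 12). The document does not define a month in days, so three readings are used. The calendar reading takes 28-31 days for 1 month, 89-92 for 3 months and 181-184 for 6 months.

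| Reading | 1-month visit (day) | 3-month visit (day) | 6-month visit (day) |
|---|---|---|---|
| 4, 12 and 24 weeks | 23-33 | 79-89 | 163-173 |
| 30-day months | 25-35 | 85-95 | 175-185 |
| Calendar months | 23-36 | 84-97 | 176-189 |

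Assume that the stopped patient attends the 6-month visit. Then:

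share outside the stated period = (final visit day − stop day) / final visit day

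Stop at the 1-month visit:
- weeks: (163 − 33)/163 = 79.8% to (173 − 23)/173 = 86.7%
- 30-day months: (175 − 35)/175 = 80.0% to (185 − 25)/185 = 86.5%
- calendar months: (176 − 36)/176 = 79.5% to (189 − 23)/189 = 87.8%

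Stop at the 3-month visit:
- weeks: (163 − 89)/163 = 45.4% to (173 − 79)/173 = 54.3%
- 30-day months: (175 − 95)/175 = 45.7% to (185 − 85)/185 = 54.1%
- calendar months: (176 − 97)/176 = 44.9% to (189 − 84)/189 = 55.6%

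Overall this is about 80-88% and 45-56%. The extremes are outer bounds, because the shortest month and the longest half-year need not coincide. With equal months of 30.44 days and no window, the shares are 152.2/182.6 = 83% and 91.3/182.6 = 50%.

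For a patient who completes the course, the interval from day 168 to the final visit is −5 to +5 days if 6 months means week 24. It is 7 to 21 days on the other two readings (175 − 168 = 7; 189 − 168 = 21).

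**Effect on the proportion with an event.** One patient is 1/15 = 6.7 percentage points or 1/10 = 10 points. The proportion moves only if the patient had no event on drug and a non-serious event afterwards. A patient already counted for an on-drug event does not move it, although the types of event reported may change.

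**The case against.** The strongest reply is that the recording sentence does not say *only* during administration. The sentences around it cover any adverse event and any serious one with no end date, and asking patients to call makes little sense if the calls go unrecorded. On this view the rule is unclear but excludes nothing. That stands in part: staff may well record later events. But a stated period that ends with the drug is more than silence, and nothing obliges anyone to record or count a non-serious event after it.

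A second reply is that an on-drug frequency is a coherent answer to an endpoint about the safety of the drug. That is so, but the plan does not say that end-point c) is limited in this way.

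A third reply is that the percentages are shares of time at hypothetical stop dates, with no stopping rate in the documents, and depend on stopped patients attending the 6-month visit. All of this is correct. Item 12 does not exempt such patients, but it does not address them either.

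A reader might infer more than the text supports:

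- *That serious events after a stop go unreported.* The serious-event sentence has no time limit.
- *That 80-88% of events would be lost.* The figure is a share of time, not of events.
- *That every patient stopped for an adverse event shifts the proportion.* Such a patient is already counted through the on-drug event.
- *That having no data monitoring committee deepens the gap.* A committee reviews records; it does not create them.

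**Conclusion.** The point holds as a limited, inexpensive improvement to the safety plan. Under the stated rule, non-serious events after the last dose can be left out of end-point c), mainly for patients who stop early.

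The size depends on how many patients stop, which the documents do not give. For a patient who stops at 1 or 3 months and attends the 6-month visit, about 80-88% or 45-56% of the time to that visit is outside the stated period, whichever reading of a month is used. With no early stops the gap is near zero if 6 months means week 24. The 6.7 to 10 point shift applies only to a patient with no on-drug event and a later non-serious one.

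The documents do not support calling this a deliberate exclusion of later events or a failure of serious-event reporting. Sample size and efficacy tests are unaffected.

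**What to change.** Change the recording sentence so that adverse events are recorded for every patient, including those who stop early, from the first injection through the planned 6-month visit, or through the last injection if that is later. Report end-point c) separately for events on drug and events after stopping.

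Any safety follow-up beyond that visit is for the sponsor and investigator to set. The change takes no position on dose, course length or when to stop the drug.

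The cost is protocol wording and slightly more recording at visits already planned. The main drawback is that events after stopping may reflect the disease or other treatment. Separate reporting deals with this by keeping the on-drug frequency intact.

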## **Consent**

Consent will be obtained in a clinical setting by a member of the study team at the time of planned enrollment. Children under the age of 18 and non-English speaking subjects will not be enrolled in this clinical study.

